#### **9.2.1.2 Values at each assessment visit and changes from baseline for ESR, DAS28-ESR, CDAI, and joint counts (TJC, SJC)**

At each visit, all the efficacy parameters will be assessed.

The **erythrocyte sedimentation rate (ESR)** is measured in mm/hr. This laboratory test will be performed in a local medical laboratory.

The DAS28 is a combined index for measuring disease activity in RA. The index includes the assessment of 28 joints for swelling and tenderness, acute phase response (ESR or CRP), and general health status. For this study, ESR will be used to calculate the DAS28 score. The index is calculated using the following formula:

$$\mathbf{DAS28-ESR} = 0.56 \times \sqrt{(TJC28)} + 0.28 \times \sqrt{(SJC28)} + 0.70 \times \ln(ESR) + 0.014 \times PtGA$$

where **TJC28** is the tender joint count on 28 joints, **SJC28** is the swollen joint count on 28 joints,  $\ln$  is the natural log, ESR is the erythrocyte sedimentation rate (mm/hour), i.e., patient's global assessment of disease activity (PtGA using a 100 mm VAS). The 28 joints to be assessed are detailed in Appendix B.

The DAS28 scale ranges from 0 to 10, where higher scores represent higher disease activity.

The **CDAI** is a combined index for measuring disease activity in RA that does not include a laboratory test. It is calculated as follows:

$$\text{CDAI} = \text{TJC28} + \text{SJC28} + \text{PtGA (in cm)} + \text{PhGA (in cm)}$$

where TJC28 is the tender joint count on 28 joints, SJC28 is the swollen joint count on 28 joints, PtGA is patient's global assessment of disease activity (100mm VAS), and PhGA is the physician's global assessment of disease activity (100mm VAS). The 28 joints to be assessed are detailed in Appendix B.

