### Infections

Biologics including sarilumab have been associated with an increased risk of infections. Physicians should then exercise caution when considering the use of sarilumab in patients with a history of recurring infections or with underlying conditions (e.g., diabetes mellitus) which may predispose patients to infections. Sarilumab should not be administered in patients with active infection. Therefore patients with active current infection or a history of recurring infection (including but not limited to active TB or history of incompletely treated TB and atypical mycobacterial disease, hepatitis B and C, and herpes zoster) will be excluded from the study.

The effects of sarilumab on acute reactants, neutrophils, and the signs and symptoms of infection should be considered when evaluating a patient for a potential infection. Any infection should be reported by the Investigator as an adverse event and a corresponding eCRF form should be filled in (type of infection, treatment with antibiotics if any with route of administration).

As all biologics, sarilumab may induce immunosuppression, increasing the risk of reactivation of latent TB. As a precautionary measure, patients with active TB will be excluded from the study. For inclusion, patient with a past history of TB could be included only if there is a documented confirmation medically validated by the Investigator that the patient was adequately treated and does not meet any of the TB-related exclusion criteria, notably based on physical examination, negative chest X-ray and TB test over the Screening period.

**NOTE:** in case of latent TB infection the patient may be included if a subsequent appropriate anti TB treatment is initiated since at least 3 weeks

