##### **11.4.2.2 Secondary analyses**

All secondary parameters will be described. For continuous variables, the number of available data, mean, standard deviation, median and range (minimum, maximum) will be provided. Categorical variables will be summarized using number and percentage of patients. Patients with missing data will not be included in the calculation of percentages. 95% CI will be provided.

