APPENDIX A: DERIVED DATA

The derived data are variables which are calculated from the raw data in the CRF/eCRF and not included in the database (e.g.: AUC, total score, duration, summary value from repeated observations, study exposure, study drug exposure, study drug cumulative dose, etc.).

The formula used for derived data should be provided and examples may be necessary to clarify the calculation. The strategy for missing data must be specified in the calculation of derived data (e.g.: the minimum number of observations required to calculate an average score, handling incomplete dates).

All references used to calculate the derived data should be mentioned below.

The following derived data will be calculated and included in the listings:

(1) SUBGROUPS DECISION

Treatment started before screening visit and ongoing at screening visit	Prescribed treatment at baseline
csDMARDs	Sarilumab + csDMARDs
Biological therapy	Sarilumab + csDMARDs
csDMARDs or biological therapy	Sarilumab in monotherapy

(2) DAS28-ESR

$DAS28-ESR = 0.56 \times \sqrt{TJC28} + 0.28 \times \sqrt{SJC28} + \ln(ESR) + 0.014 \times PtGA$ (in mm)

Where:

- ln is the natural logarithm
- SJC is the swollen joints
- TJC is the tender joints
- PtGA is the patient's global assessment of disease activity (using a 100 mm VAS)
- ESR is the erythrocyte sedimentation rate (mm/h)

(3) CDAI

$CDAI = TJC28 + SJC28 + PtGA(\text{in cm}) + PhGA(\text{in cm})$

Where:

- SJC is the swollen joints
- TJC is the tender joints
- PhGA is the physician's global assessment of disease activity (using a 100 mm VAS)
- PtGA is the patient's global assessment of disease activity (using a 100 mm VAS)

(4) BMI

BMI (kg/m²) will be derived as $\text{Weight (kg)} / [\text{Height (cm)} / 100]^2$ and rounded to the nearest decimal.

(5) Time between baseline and initial diagnosis (years)

Time between baseline and initial diagnosis in years will be calculated as $(\text{initial diagnosis date} - \text{baseline visit date} + 1) / 365.25$.

(6) Changes from baseline (V2)

Absolute variation (points) from baseline will be calculated as a difference from baseline (e.g. assessment at the visit – assessment at baseline).

Relative variation (%) from baseline will be calculated as: $((\text{assessment at the visit} - \text{assessment at baseline}) / \text{assessment at baseline}) * 100$.

If necessary, evolution will be presented according to decision tables from Appendix B.

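### DAS28-ESR has no rule for an ESR of 0, where the score is undefined; affected patients would leave the remission and low-disease-activity rates, with a probable but uncertain downward bias

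*SAP*

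**What the plan says.** Protocol 9.2.1.2 defines DAS28-ESR as 0.56·√TJC28 + 0.28·√SJC28 + 0.70·ln(ESR) + 0.014·PtGA. SAP Appendix A (2) repeats the formula, but its ESR term is ln(ESR) with no coefficient. On the logarithm the SAP adds only that "ln is the natural logarithm". Neither document gives a floor, an offset or a substitute value for ESR.

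On how ESR is obtained, Protocol 9.2.1.2 says: "This laboratory test will be performed in a local medical laboratory". No reporting limit is given.

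The rules that would then apply are these:

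- The introduction to SAP Appendix A requires the missing-data strategy to be specified for derived data. RAID, HAQ-DI and IPAQ each have one. DAS28-ESR has none.
- SAP 6.4 carries the last value forward only after treatment discontinuation for lack of efficacy or an adverse event. In all other cases nothing is replaced.
- Protocol 11.4.2.2, for secondary categorical endpoints: "Patients with missing data will not be included in the calculation of percentages".
- SAP 6.2 excludes impossible or implausible outliers, without saying whether an ESR of 0 is one.

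Protocol 9.2.1.3 sets remission at DAS28-ESR below 2.6 and low disease activity at 3.2 or below, reported at W12 and W24.

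**The concern.** An ESR of 0 is an observed result, and a favourable one. Under the formula as written it yields no score, and the general rules then treat the patient as missing. If this happens, the patients lost are selected on a component of the score itself, so the loss is not random with respect to the endpoint.

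The drug gives a reason to look at the low end of ESR. Sarilumab blocks IL-6 signalling, and the infection guidance in Protocol 10.6 says that "The effects of sarilumab on acute reactants, neutrophils, and the signs and symptoms of infection should be considered". Low values on treatment are therefore foreseeable.

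The DAS28-ESR remission and low-disease-activity rates, the mean DAS28-ESR and its change, and the association models in SAP 5.3.2.5 that use DAS28-ESR as a covariate would all lose these records. CDAI would keep them, so the two indices would be reported on different denominators.

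**Working it through.** **1. The formula at ESR = 0.** ln(0) has no finite value (the limit is minus infinity), with or without the 0.70 coefficient. No score can be computed.

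**2. Who would be lost.** Take ESR = 1 mm/h as an illustrative floor (an assumption; the documents give none). Then ln(1) = 0 and the score is 0.56·√TJC + 0.28·√SJC + 0.014·PtGA:

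| TJC, SJC, PtGA (mm) | Sum | Score | Status |
|---|---|---|---|
| 1, 1, 20 | 0.56 + 0.28 + 0.28 | 1.12 | remission |
| 4, 4, 30 | 1.12 + 0.56 + 0.42 | 2.10 | remission |
| 6, 4, 50 | 1.37 + 0.56 + 0.70 | 2.63 | low disease activity only |
| 10, 8, 60 | 1.77 + 0.79 + 0.84 | 3.40 | neither |

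Most patients with few residual joints would be in remission. Patients with substantial joint counts or a high global score would not.

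**3. Effect on the remission rate.** The plan states no figure of its own to reproduce. Inputs:

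- p = 26.6%, the Week 24 DAS28-ESR remission rate on sarilumab in the monotherapy trial tabulated in Protocol 4.1.2. The 40.2% in the same section is low disease activity by DAS28-CRP and is not a comparable base.
- N = 112, the evaluable number in the protocol synopsis (140 × 0.80 = 112).
- k = patients with ESR 0 at the visit: 1, 3 or 6, which is about 1%, 3% or 5% of 112. This is an assumption.
- r = the share of those k who would be in remission: 1, 0.5 or 0. This is also an assumption.

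Reported rate = (p·N − r·k)/(N − k), with p·N = 0.266 × 112 = 29.792:

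| k | All in remission | Half | None |
|---|---|---|---|
| 1 | 28.792/111 = 25.9% | 29.292/111 = 26.4% | 29.792/111 = 26.8% |
| 3 | 26.792/109 = 24.6% | 28.292/109 = 26.0% | 29.792/109 = 27.3% |
| 6 | 23.792/106 = 22.4% | 26.792/106 = 25.3% | 29.792/106 = 28.1% |

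Against 26.6%, the loss is 0.7, 2.0 or 4.2 points if all are remitters and 0.2, 0.6 or 1.3 points if half are. If none are, the rate rises by 0.2, 0.7 or 1.5 points.

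For scale, the 95% CI half-width at 26.6% and n = 112 is 1.96 × √(0.266 × 0.734/112) = 8.2 points.

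**4. If the patient is not dropped.** SAS ranks a missing number below every real number, so an unguarded test of score < 2.6 would count an undefined score as remission. If none of the k patients were really in remission, the rate would be (29.792 + k)/112 = 27.5%, 29.3% or 32.0% for k = 1, 3 or 6.

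**5. The ESR term in the same SAP line.** Without the 0.70 coefficient the SAP score exceeds the protocol score by 0.30·ln(ESR): 0.48 at ESR 5, 0.69 at 10 and 0.90 at 20. With TJC 1, SJC 1, PtGA 20 and ESR 5, the protocol formula gives 1.12 + 0.70 × 1.61 = 2.25 (remission) and the SAP formula gives 1.12 + 1.61 = 2.73 (not remission). SAP 1.6, which lists modifications from the protocol, does not mention this change.

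**The case against.** The strongest objection is that occurrence is not shown. No section reports an ESR of 0, an ESR distribution on treatment or a laboratory limit. The sentence in Protocol 10.6 is a caution about recognising infection; it says that acute reactants are affected, not that ESR reaches 0. This stands, and it is why k is an assumption above.

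Direction is also open. A reader might infer that the plan certainly removes the strongest responders and so understates efficacy. The documents do not support that. ESR is one of four components, so a patient with ESR 0 can still be out of remission, in which case dropping that patient raises the rate. The plan also never says outright that an incomputable score is to be treated as missing; an unguarded flag would bias the rate upward or leave it unchanged. The written denominator rule makes exclusion the natural reading, and step 2 makes a downward bias the likelier outcome, but no more than that.

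Safeguards exist. SAP 3.1 reports available and missing counts for every variable, SAP 6.2 provides for an outlier search before lock, SAP 8.3 includes review of log notes and subject counts, and CDAI is reported alongside. They make an unnoticed loss unlikely, but none supplies a rule. The decision would be made once the values had been seen, in an open-label study.

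Finally, the obvious repair can do harm if applied too widely. If a local laboratory reported a result as <5 (an assumption), setting it to 1 mm/h could lower the protocol score by up to 0.70 × ln(5) = 1.13 points and move patients into remission. That objection stands and limits the fix.

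**Conclusion.** The gap is real: the score is undefined at ESR = 0, Appendix A's own requirement is not met for DAS28-ESR, and the general rules would drop the patient from the DAS28-ESR percentages. A downward bias in remission and low disease activity is probable, not certain.

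The size depends on two quantities that the documents do not give: how often ESR is 0, and how many of those patients are in remission. Over 1 to 6 patients of 112, the remission rate moves from 26.6% to between 22.4% (six lost, all remitters) and 28.1% (six lost, none remitters). Each of these shifts is smaller than the 8.2-point half-width of the confidence interval.

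The affected endpoints are secondary or exploratory. The secondary analyses are descriptive, and the RAID primary endpoint and CDAI contain no ESR. This is a minor issue, worth correcting because the correction is simple. The missing 0.70 coefficient in the same line affects every score with an ESR other than 1 and has to be reconciled in any case.

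**What to change.** Before database lock, amend SAP Appendix A (2) as follows:

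1. A recorded ESR of 0, or below 1 mm/h, is set to 1 mm/h in the DAS28-ESR formula, so that its log term is 0.
2. A result reported only as below a higher laboratory limit is handled by a separate prespecified rule based on that limit, with a sensitivity analysis. It is not set to 1.
3. The remission and low-disease-activity flags are left missing when the score is missing, so that no patient is classified by software default.
4. The number of values touched by rules 1 and 2 is reported per visit.
5. The SAP's ln(ESR) is reconciled with the protocol's 0.70·ln(ESR).

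A matching sentence in Protocol 9.2.1.2, if that section is amended, would keep the documents aligned. The cost is a few sentences in the SAP, a few lines of code, one small count table and, only if such results occur, one sensitivity run. No new data are needed.

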5. ANALYSIS OF PATIENT DATA

5.1. ANALYSIS VARIABLES

5.1.1. Patients' characteristics

- **Demography**

- Age at baseline (years)
- Sex (Female / Male)

- **Physical examination and vital signs at baseline**

- Height (cm)
- Weight (kg)
- Body Mass Index (BMI)^{DD} (kg/m²)
 - As quantitative
 - In classes:
 - Underweight (<18.5)
 - Normal (healthy) weight ([18.5; 25[)
 - Overweight ([25.0; 30[)
 - Obese (≥30)
- Abdominal girth (cm)
- Blood pressure
 - Systolic (mmHg)
 - Diastolic (mmHg)
- Heart rate (beats/min)

- **Medical and surgical history**

- Medication history for rheumatoid arthritis

- Time from RA diagnosis (years)^{DD}
- Patient previously treated with conventional synthetic DMARDs (Yes/No)
- Patients previously treated with biological therapies and targeted synthetic DMARDs at baseline (Yes/No)
- Patients previously treated with corticosteroids (Yes/No)
- Patient currently treated with NSAIDs, analgesics (Yes/No)
- Patient currently receiving other treatments for their RA (Yes/No)
- Patient treated with other treatment (other than those for RA) (Yes/No)

Conventional synthetic DMARDs, biological therapies and targeted synthetic DMARDs, corticosteroids and NSAIDs, analgesics will be presented according to their status at baseline: ongoing or ended at baseline.

- Medical history and associated diseases

- Patient having experienced any past or concomitant diseases (clinically significant) (Yes/No)

If yes, past or concomitant diseases will be presented by System Organ Class (SOC) and Preferred Term (PT).

➤ Surgical history in relation with rheumatoid arthritis

- Patient having any surgical history in relation with rheumatoid arthritis (Yes/No)
If yes, surgical history will be presented by SOC and PT.

- **Characteristics of rheumatoid arthritis**

- Anti-CCP (Positive/Negative/Not performed)
- Rheumatoid factor (Positive/Negative//Not performed)
- Signs of structural joint involvement (Yes/No)
- At least one rheumatoid nodule (Yes/No)
 - If yes:
 - Size of the largest nodule at screening and at the last measure (mm)
 - Changes from baseline^{DD}
 - Time between measures of the rheumatoid nodule (months)^{DD}
- Chest X-Ray (Normal or with a non-clinically-significant abnormality / Abnormal with a clinically-significant abnormality / not performed)

- **Evaluation of rheumatoid arthritis activity**

- Visual Analogue Scale (VAS) Global Assessment of disease activity (mm) by physician (0=no pain to 100-maxima pain imaginable)

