5.1.5.3. To explore patients' profiles

Patients' profiles will be explored using the same analyses performed for the analysis of baseline data. Association between cognitive troubles and patients' characteristics will be tested. Cognitive troubles will be evaluated by the MATHyS cognition score as qualitative variable (using the tertiles: <1st tertile, [1st tertile; 2nd tertile[, ≥ 2nd tertile).

Characteristics (at baseline) to be tested are:

- Age in quantitative or in classes (using quartiles) if linearity is not verified
- Sex (Female / Male)
- BMI in classes (Normal/Abnormal i.e Underweight or Overweight or Obese)
- Time between baseline and initial diagnosis (years) in quantitative or in classes (using quartiles), if linearity is not verified
- DAS28-ESR in quantitative or in classes (using quartiles), if linearity is not verified
- Patient previously treated with biological therapies and targeted synthetic DMARDs (Yes/No)
- Patient currently treated with corticosteroids for his/her RA (Yes/No)
- Patient currently treated with NSAIDs, analgesics (Yes/No)
- Patient having experienced any past or concomitant diseases (clinically significant) (Yes/No)
- Depression evaluated by HADS (Yes/No). If HADS depression = 'Normal' then Depression='No'. Else if HADS depression = 'Boderline abnormal' or 'Abnormal' then Depression='Yes'
- Anxiety evaluated by HADS (Yes/No). If HADS anxiety = 'Normal' then Anxiety='No'. Else if HADS anxiety = 'Boderline abnormal' or 'Abnormal' then Anxiety='Yes'
- Fatigue (FACIT-F total score) in quantitative or in classes (using quartiles), if linearity is not verified
- Global Assessment of disease activity (mm) by patient (0-no pain to 100-maxima pain imaginable) in quantitative or in classes (using quartiles), if linearity is not verified
- Global Assessment of disease activity (mm) by physician (0-no pain to 100-maxima pain imaginable) in quantitative or in classes (using quartiles), if linearity is not verified
- MATHyS global score in quantitative (only descriptive, not in the model due to collinearity with cognition score)
- Positive Anti-CCP (Yes/No)
- Positive rheumatoid factor (Yes/No)

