5.3. STATISTICAL METHODS

5.3.1. Disposition of patients

Key information of the study will be presented (First patient first visit, last patient last visit, first patient last visit, last patient last visit, number of centers with at least one patient included, enrollment duration (months)^{DD}).

Disposition of patients will be depicted for patient status and patient analysis populations. The total number of patients for each of the following categories will be described:

- Enrolled patients

- Patients failed to be enrolled and the reason for non-enrollment
- Safety population
- ITT population
- Per-Protocol population.

Summary tables and flowcharts will present the number and percentage of subjects who not entered in the study and reason for non-enrolment into the registry will be presented overall (non-compliance with inclusion / exclusion criteria, patient's refusal of consent).

Summary tables and flowcharts will present the number of subjects at each assessment and the number of subjects by population. Follow-up duration^{DD} (weeks) will be calculated overall. The number and percentage of subjects who withdrew from the study and the reasons for premature withdrawal will be presented overall (adverse event, death, treatment inefficacy, major protocol deviations, consent withdrawal, lost to follow-up or other reason). Time between baseline and premature withdrawal^{DD} (weeks) will also be presented.

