(7) Duration of IMP exposure (week)

The duration of IMP exposure is defined as follows: $(\text{last dose date} - \text{first dose date} + 14 \text{ days}) / 7$ regardless of unplanned intermittent discontinuations.

(8) Enrollment duration (months)

Enrollment duration (months) will be calculated as: $((\text{date of last patient last visit} - \text{date of first patient first visit}) + 1) / 30.4375$.

(9) Follow-up duration (weeks)

Follow-up duration in weeks will be calculated as: $((\text{date of last contact with the patient} - \text{date of baseline}) + 1) / 7$.

(10) Time between baseline and premature withdrawal (weeks)

Time between baseline and premature withdrawal in weeks will be calculated as $((\text{withdrawal date} - \text{baseline visit date}) + 1) / 7$.

(11) Time between measures of the rheumatoid nodule (months)

Time between measures of the rheumatoid nodule (months) will be calculated as: $(\text{date of the last measure of the rheumatoid nodule} - \text{date of screening}) + 1) / 30.4375$.

(12) RAID

The RAID is calculated based on 7 Numerical rating scales (NRS) questions (see Appendix C). Each NRS is assessed as a number between 0 and 10. The 7 NRS correspond to pain, function, fatigue, sleep, emotional well-being, physical well-being, and coping/self-efficacy.

Calculation: RAID final value = $(\text{pain NRS value (range 0-10)} \times 0.21) + (\text{function NRS value (range 0-10)} \times 0.16) + (\text{fatigue NRS value (range 0-10)} \times 0.15) + (\text{phys well being NRS value (range 0- 10)} \times 0.12) + (\text{sleep NRS value (range 0-10)} \times 0.12) + (\text{emotional well being NRS value (range 0-10)} \times 0.12) + (\text{coping NRS value (range 0-10)} \times 0.12)$.

Thus, the range of the final RAID value is 0-10 where higher figures indicate worse status. Missing data imputation: If one of the 7 NRS values composing the RAID is missing, the imputation is as follows:

- a. calculate the mean value of the 6 other (non-missing) NRS (range, 0-10)
- b. impute this value for the missing NRS
- c. Then, calculate the RAID as explained above. If 2 or more of the NRS are missing, the RAID is considered as missing value (no imputation).

See: http://pitie-salpetriere.aphp.fr/psaid/raid_psaidd_quest_home.php

(13) **Hospital Depression Scale (issue from HADS)**

Total score of depression is the sum of tick boxes of columns D (see Appendix D). The range of the total score of depression value is 0-21.

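### Two SAP duration formulas give wrong output if programmed as written: disease duration comes out negative, and the enrolment duration is total study duration

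*SAP*

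**What the plan says.** **Disease duration.** SAP Appendix A (5) reads "Time between baseline and initial diagnosis in years will be calculated as", followed by a formula that takes the initial diagnosis date, subtracts the baseline visit date, adds 1 and divides by 365.25. The variable has two uses:

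- SAP 5.1.1 lists it among the patient characteristics, flagged as derived data, under the label "Time from RA diagnosis (years".
- SAP 5.1.5.3 lists it as a candidate factor for the patient-profile analyses: "Time between baseline and initial diagnosis (years) in quantitative or in classes (using quartiles), if linearity is not verified". SAP 5.3.2.5.3 then uses it in the factorial analysis for mixed data and in the logistic regression on MATHyS cognition tertiles.

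**Enrolment duration.** SAP Appendix A (8) reads "Enrollment duration (months) will be calculated as", followed by last patient last visit minus first patient first visit, plus 1, divided by 30.4375. SAP 5.3.1 reports the result as key study information. The dates listed beside it are "First patient first visit, last patient last visit, first patient last visit, last patient last visit": one date appears twice, and last patient first visit does not appear.

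**The concern.** Appendix A is the programming specification for derived variables, and both items give the wrong quantity when followed exactly.

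Inclusion requires established RA with inadequate response or intolerance to a csDMARD or an anti-TNF (protocol 7.1, I 01 and I 03). Diagnosis therefore precedes baseline, and item (5) subtracts the later date from the earlier one. The baseline table would show negative years, and the profile model would report this covariate's association in the wrong direction.

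Item (8) includes the treatment and follow-up of patients already enrolled. The resulting enrolment period would be too long but would not look odd, so an output check could easily miss it.

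**Working it through.** The documents state no value for either duration, so there is no planned figure to reproduce. The check evaluates each formula as written.

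**Item (5).** Let D be the diagnosis date and B the baseline date. As written, X' = (D - B + 1)/365.25. In the correct order, X = (B - D + 1)/365.25. The baseline date is assumed to be 1 June 2018, for illustration only.

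| Diagnosis before baseline | D - B (days) | As written (years) | Dates reversed (years) |
|---|---|---|---|
| 1 day | -1 | 0.000 | 0.005 |
| 1 year | -365 | -0.997 | 1.002 |
| 10 years | -3652 | -9.996 | 10.001 |
| 20 years | -7305 | -19.997 | 20.003 |

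For the 10-year case, (-3652 + 1)/365.25 = -9.996, against (3652 + 1)/365.25 = 10.001. The absolute values differ by 3653 - 3651 = 2 days, which is immaterial. The sign is what is wrong.

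Algebraically, X' = -X + 2/365.25. In a logistic model, a + bX = (a + 2b/365.25) - bX'. The slope changes sign, so the odds ratio becomes its reciprocal, while the likelihood and the p-value for the slope stay the same. If quartile classes are used, the groups hold essentially the same patients (ties at cut-points aside) in reverse order, so the class labelled lowest holds the longest-standing disease. The overall test of the factor does not change.

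The other elapsed-time items in Appendix A, (7) and (9) to (11), all subtract the earlier date from the later. Item (5) is the only reversed one, so this is not a convention of the document.

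**Item (8).** Protocol 6.2.2 places the last visit at Week 26-28 for a patient who does not enter the LTE, and at Week 50-52 at most for one who does. Protocol 6.2.1 allows up to 4 weeks of screening before that. Excess in months = weeks x 7 / 30.4375, for a last-entered patient who completes the schedule and whose last visit closes the trial:

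| Case | From baseline | With 4 weeks of screening |
|---|---|---|
| No LTE | 26-28 weeks = 6.0-6.4 months | 30-32 weeks = 6.9-7.4 months |
| Full LTE | 50-52 weeks = 11.5-12.0 months | 54-56 weeks = 12.4-12.9 months |

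As an illustration, an assumed enrolment period of 12 months would be reported as 18.0-19.4 months without the LTE (12 + 5.98 to 12 + 7.36), or 23.5-24.9 months with it (12 + 11.50 to 12 + 12.88).

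**The case against.** The best defence of item (5) is that the error would reveal itself. The label in SAP 5.1.1 makes the intended direction plain, and SAP 8.3 requires outputs to be reviewed for nonsensical values; a negative mean disease duration is one. This makes it less likely that the baseline table would be published wrong. It does not correct the formula. SAP 8.3 also asks for consistency with the SAP, so a programmer who corrects the sign departs from the specification. An inverted odds ratio or a reversed quartile order is harder to see than a negative mean.

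A reader might infer that variable selection or significance in the profile model is distorted. It is not: the algebra above leaves p-values and fit as they were. The model is exploratory, and the primary RAID analysis in SAP 5.3.2.2 does not use disease duration.

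For item (8), the fair objection is that the figure is descriptive and enters no efficacy or safety analysis. That stands. It is also fair that the excess is not one fixed quantity. The LTE case applies only while sarilumab is not commercially available in France (protocol 7.3). An early withdrawal by the last patient would shorten the excess. The closing visit could also belong to an earlier patient still in the LTE. A single range of 26 to 52 weeks would merge two separate cases and is not what the protocol gives.

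Finally, a reader might say that the reported figures are wrong. The documents contain no results, so they support only the statement that the figures would be wrong if programmed as written.

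**Conclusion.** Both formulas are wrong as written, and nothing elsewhere in the SAP corrects them; the table of changes from the approved version (SAP 1.7) mentions neither.

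- Item (5) gives negative disease durations whose size is right to within 2 days. The consequences are a wrong baseline table, a reversed quartile order and an inverted odds ratio for one exploratory covariate.
- Item (8) reports total study duration under an enrolment label. The size of the excess depends on the conditions shown with the calculation: who makes the last visit, whether that patient completes the schedule, and whether that patient enters the LTE.

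The duplicated date in SAP 5.3.1 suggests that item (8) began as a copying slip. The point is minor: no primary or safety conclusion depends on either variable.

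**What to change.** - Item (5): (baseline visit date - initial diagnosis date + 1) / 365.25.
- Item (8): (date of last patient first visit - date of first patient first visit + 1) / 30.4375, with the same type of visit at both ends. First visit fits SAP 3.2.1, which defines enrolled patients by screening and signed consent. Pairing a first visit at the start with an inclusion visit at the end would add up to 4 weeks of screening.
- SAP 5.3.1: replace the duplicated last patient last visit with last patient first visit.
- If total study duration is also wanted, report it under its own label.

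The cost is a few text edits to the SAP and the matching lines of code. No analysis method changes.
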